### **8.3.2. Method of Detecting AEs and SAEs**

The method of recording, evaluating, and assessing causality of AE and SAE and the procedures for completing and transmitting SAE reports are provided in Appendix 3.

Care will be taken not to introduce bias when detecting AEs and/or SAEs. Open-ended and nonleading verbal questioning of the participant is the preferred method to inquire about AE occurrences.

### **8.3.3. Follow-up of AEs and SAEs**

After the initial AE/SAE report, the investigator is required to proactively follow each participant at subsequent visits/contacts through the last study visit. All AEs (regardless of relationship to study intervention) and SAEs determined not to be study intervention related (ie, not related and unlikely related) will be followed through the last study visit and be noted as “continuing” if not resolved at this visit.

All SAEs considered study-drug related will be followed until resolution, stabilization, is determined to be irreversible by the investigator, the participant is lost to follow-up (as defined in [Section 7.3](#)), or it has been determined that the study treatment is not the cause of the AE/SAE, whichever occurs first. AE/SAE reporting will end after the participant initiates alternative cancer treatment.

Further information on follow-up procedures is given in [Appendix 3](#).

### **8.3.4. Regulatory Reporting Requirements for SAEs**

- Prompt notification (eg, 24 hours of becoming aware of the event) by the investigator to the Sponsor of a SAE is essential so that legal obligations and ethical responsibilities toward the safety of participants and the safety of a study intervention under clinical investigation are met.
- The Sponsor has a legal responsibility to notify both the local regulatory authority and other regulatory agencies about the safety of a study intervention under clinical investigation. The Sponsor will comply with country-specific regulatory requirements relating to safety reporting to the regulatory authority, Institutional Review Boards (IRBs), and investigators.

- Investigator safety reports must be prepared for suspected unexpected serious adverse reactions (SUSARs) according to local regulatory requirements and Sponsor policy and forwarded to investigators as necessary.
- An investigator who receives an investigator safety report describing a SAE or other specific safety information (eg, summary or listing of SAEs) from the Sponsor will review and then file it along with the IB and will notify the IRB, if appropriate according to local requirements.

#### **8.3.5. Pregnancy**

- Details of all pregnancies in female participants and, if indicated, female partners of male participants will be collected after the start of study intervention and until EOT visit.
- If a pregnancy is reported, the investigator should inform the Sponsor within 24 hours of learning of the pregnancy and should follow the procedures outlined in [Appendix 4](#).
- Abnormal pregnancy outcomes (eg, spontaneous abortion, fetal death, stillbirth, congenital anomalies, ectopic pregnancy) are considered SAEs.

#### **8.3.6. Safety Committees**

Two safety committees will be employed during this study: the Dose Committee and the ISMC.

The Dose Committee, composed of Sponsor representatives and investigators, will evaluate the C1 safety data after the 28-day DLT window once the third participant in each dose cohort has completed. This committee will make the final decision on dosing for the next cohort, taking in to account all available safety data including any available data on any fourth participant enrolled in a dose cohort, if applicable ([Section 4.1.1.1](#)). In addition, all available efficacy, safety, and PK/PD data will be used to determine whether Dose-Expansion may commence at the end of each Dose-Escalation Cohort.

In addition to the safety data reviews for dose escalation and cohort expansion, the ISMC will review emergent safety data from the RMC-4630 program after approximately every 3 months or after the first 6 participants have completed 2 cycles, whichever is earlier. Subsequently the committee will review data approximately every 3 months. The committee may adjust the timing of the review from the defined schedule, depending on the rate of enrollment. The committee will consist of the Medical Monitor, Drug Safety Monitor, and a Biostatistician. Relevant findings from the safety data reviews will be discussed with the study investigators. Based on the ongoing safety assessments, the committee may recommend changes in dosing regimen or other alterations to study procedures. The Medical Monitor or Drug Safety Monitor may convene a meeting sooner should any concerns arise from review of data or from the investigators.

**8.4. Treatment of Overdose**

For this study, any dose of RMC-4630, cobimetinib, or osimertinib, 1.5× greater than the intended dose per administration or 2 administrations at the intended dose or more within <12 hours for QD dosing or < 24 hours for intermittent dosing will be considered an overdose. Similarly, for twice weekly D1, D2 dosing schedule, 2 administrations of the same agent <12 hours apart will be considered an overdose. There is no clinical experience with an overdose of RMC-4630, cobimetinib, or osimertinib in human clinical trials. No experiments have been performed to determine whether the effects of an overdose can be reversed, and there are no known antidotes.

Revolution Medicines does not recommend specific treatment for an overdose. The individual should be monitored clinically, and supportive care should be undertaken as clinically indicated.

In the event of an overdose, the investigator should:

1. Halt the dispensation and administration of the involved medication. The investigator may also hold the second medication based on his/her clinical judgement.
2. Contact the Medical Monitor immediately.
3. Closely monitor the participant for any AE/SAE, ECG, and laboratory abnormalities (blood glucose, liver function tests, creatinine, blood urea nitrogen (BUN), CPK, and complete blood count) until RMC-4630 and/or cobimetinib can no longer be detected systemically.
4. Obtain a plasma sample for PK analysis within 1 to 2 days from the date of the last dose of study intervention if requested by the Medical Monitor (determined on a case-by-case basis).
5. Document the quantity as well as the duration of the overdose in the eCRF.
6. Decisions regarding resumption of study intervention will be made by the investigator in consultation with the Medical Monitor based on the clinical evaluation of the participant.

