### **6.1.2. RMC-4630 and Osimertinib (Study in US Only)**

During the Dose Escalation Component, RMC-4630 will be administered orally on an intermittent basis with twice weekly dosing on D1 and D2 with a starting dose of 140 mg. Alternative dose schedule for RMC-4630 including D1D4 dosing may be explored depending on emerging data from this study and other RMC-4630 studies. Osimertinib will be dosed orally on the approved monotherapy dose and schedule of 80 mg once daily. The tablets and capsules should not be crushed or chewed. The participant should administer the study intervention approximately the same time every day except for clinic visit days as listed in the SoA (Section 1.3).

Dosing in the Dose-Expansion Component of RMC-4630 will be determined from the respective Dose-Escalation Component.

The participant is expected to administer a dose twice weekly on D1 and D2 (or D1D4 if an alternative schedule is implemented) except clinic visit days as listed in SoA. On these clinic visits, the participant should await instruction from the study staff to coordinate with the timing of PK and/or biomarker sampling.

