## 6.4. Study Intervention Compliance

### 6.4.1. Compliance Instructions

Dosing instructions will be provided to the participant, and participant compliance with study intervention will be reviewed at each visit. Compliance will be assessed by counting returned capsules (RMC-4630) and tablets (cobimetinib), in conjunction with participant diary information and participant questioning. Since Osimertinib is supplied as part of Standard of Care by local pharmacies, compliance will only be assessed by reviewing participants' diaries and questions asked during clinic visits. Refer to [Section 8.4](#) in the event a participant is suspected to have taken greater than the assigned dosage.

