**Table 16 Efficacy Analyses**

Endpoint	Statistical Analysis Methods
Primary	Not applicable
Secondary	
ORR is defined as the proportion of participants who achieve a CR or PR per RECIST v1.1. ORR and the corresponding 95% two-sided confidence interval will be derived.
 
DOR is defined as the interval from the first documentation of CR or PR to the earlier of first documentation of definitive disease progression or death due to any cause, whichever occurs first. Participants who are still alive and free from progression at the time of data cutoff date, are lost to follow-up, have discontinued from the study, or have initiated subsequent anticancer therapy will be censored at the last adequate tumor assessment. The Kaplan-Meier method will be used to estimate PFS and DOR curves and corresponding quartiles. Kaplan-Meier median will be calculated with a 2-sided 95% confidence interval.
 
Pharmacokinetics assessed by noncompartmental methods and summarized by descriptive statistics (mean or geometric mean, standard deviation, coefficient of variation, minimum, and maximum).

Exploratory	
Will be described in the statistical analysis plan finalized before database lock.
 
Absolute and percentage changes of pharmacodynamic assessments at baseline and during treatment.

Abbreviations: CR, complete response; DOR, duration of response; ORR, objective response rate; PR, partial response; RAS-MAPK, RAS-mitogen-activated protein kinase; RECIST v1.1, Response Evaluation Criteria in Solid Tumors, Version 1.1.

The secondary efficacy endpoints of ORR and DOR will be summarized for participants enrolled at the RP2D. If available, genotyping results from the central laboratory will supersede those from local tests for primary and secondary endpoints. Local results may be included in exploratory analyses.

PK parameter estimates, including but not limiting to the ones listed below, will be determined when possible for RMC-4630 and cobimetinib:

- $C_{max}$  (observed)
- $T_{max}$  (observed)
- $AUC_{0-t}$  and  $AUC_{inf}$
- $t_{1/2}$
- Accumulation ratio

Unless otherwise specified, the PK parameters will be estimated based on noncompartmental analysis methods. These estimates will be summarized descriptively by dose cohort. All PK parameters will be computed using actual elapsed time calculated relative to dose administration.

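### After an overdose of osimertinib alone, Section 8.4 ends close monitoring on clearance of RMC-4630, a drug that was not overdosed

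*Combined protocol and SAP*

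**What the plan says.** Section 8.4 (Treatment of Overdose) applies its definition to "any dose of RMC-4630, cobimetinib, or osimertinib". It adds that there is no clinical overdose experience with any of the three and no known antidote. Before the numbered steps it gives a general instruction with no stated end: "The individual should be monitored clinically, and supportive care should be undertaken as clinically indicated".

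The steps that matter here are:

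- **Step 1** stops the drug concerned. For the other drug it says "The investigator may also hold the second medication based on his/her clinical judgement".
- **Step 2** requires immediate contact with the Medical Monitor.
- **Step 3** requires close monitoring of adverse events, ECGs and a laboratory panel "until RMC-4630 and/or cobimetinib can no longer be detected systemically".
- **Step 4** asks for one plasma PK sample a day or two after the last dose, but only "if requested by the Medical Monitor (determined on a case-by-case basis").
- **Step 6** leaves resumption to the investigator in consultation with the Medical Monitor, on clinical grounds.

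Section 6.4.1 (Compliance Instructions) discusses all three drugs and sends the reader to Section 8.4 "in the event a participant is suspected to have taken greater than the assigned dosage". Section 6.1.2 sets the arm 2 regimen: RMC-4630 twice weekly, and "Osimertinib will be dosed orally on the approved monotherapy dose and schedule of 80 mg once daily".

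**The concern.** The definition names three drugs and the endpoint for close monitoring names two. The missing drug is the one that arm 2 participants take every day. For them, step 3 can point to a drug that had nothing to do with the overdose.

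Step 3 is the only readable rule for when close post-overdose monitoring stops, so what is at stake is participant safety. ECG monitoring is part of step 3, and Section 2.3.1.4 lists QTc prolongation as an osimertinib risk: among 1142 treated patients, 0.9% had a QTc above 500 msec and 3.6% had a rise above 60 msec. Those figures come from osimertinib trials, not from overdoses. They show why the endpoint is relevant, not how large any effect would be. Sample size, endpoints and analyses are not touched.

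**Working it through.** There is no figure in the plan to reproduce. The check sets the parts of the text side by side.

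**Count of drugs**

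- Drugs in the Section 8.4 definition: 3 (RMC-4630, cobimetinib, osimertinib).
- Drugs in the step 3 endpoint: 2 (RMC-4630, cobimetinib). Omitted: 3 − 2 = 1 (osimertinib).
- Study drugs in arm 2 (Section 6.1.2): 2 (RMC-4630, osimertinib). Named in step 3: 1. Omitted: 2 − 1 = 1.

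These counts describe the text, not the number of participants affected.

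**Does step 3 apply to osimertinib?** Yes. The definition names it, Table 8 lists it as an investigational product, and Section 6.4.1 refers suspected excess dosing to Section 8.4 without excluding any drug.

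**Each overdose case against the step 3 endpoint**

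| Arm | Drug overdosed | Is that drug in the endpoint? |
|---|---|---|
| 1 | RMC-4630 alone | Yes |
| 1 | Cobimetinib alone | Yes |
| 1 | Both | Yes, both |
| 2 | RMC-4630 alone | Yes |
| 2 | Osimertinib alone | **No** |
| 2 | Both | One of the two |

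The endpoint misses the overdosed drug entirely in one case: osimertinib alone, in arm 2.

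**What the rule does in that case.** Cobimetinib is not given in arm 2, so only RMC-4630 is left in the endpoint.

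- If RMC-4630 continues, as step 1 permits, the endpoint depends on ongoing RMC-4630 dosing and says nothing about osimertinib. Close monitoring could run longer than the overdose requires.
- If RMC-4630 is held, close monitoring ends when RMC-4630 has cleared. That could be before or after osimertinib has cleared.

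No half-lives can be read in the documents, so neither branch can be given a duration or a direction.

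**Is it corrected elsewhere?** No readable text ties the end of overdose monitoring to osimertinib. Sections 1.3 and 8.5 are redacted. Section 9.4.1 says PK parameters "will be determined when possible for RMC-4630 and cobimetinib". The List of Tables, however, gives Tables 2 and 3 as PK and pharmacodynamic sampling schedules that include the osimertinib arm, without readable analytes. Whether osimertinib is assayed is therefore unknown. The wording of step 3 is the same either way.

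**The case against.** The strongest reply is that step 3 is not a strict assay-based rule for any drug. It names a state but orders no test for it, and the single on-request sample in step 4 could not show when RMC-4630 or cobimetinib became undetectable either. In practice the investigator and the Medical Monitor would decide when to stop. This is fair and it lowers the weight of the point. It does not make the text right: the one endpoint the protocol states still names the wrong drug in this case.

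A second reply is that other safeguards cover the gap, and this largely stands:

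- The general instruction in Section 8.4 covers any overdosed participant and has no end date.
- Clinically significant laboratory abnormalities are repeated until they settle (Section 8.2.6).
- Adverse events are collected to the safety or end-of-treatment visit, and drug-related SAEs are followed further (Sections 8.3.1 and 8.3.3).
- Safety assessments, including ECGs, continue at regular intervals (Section 2.3.2).

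What remains uncovered is how long the closer monitoring lasts.

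A third reply is that the scope is narrow: an overdose of osimertinib alone, in a US-only arm planned for 24 participants in total. That also stands.

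A reader might infer that participants who overdose on osimertinib would be released from monitoring too early. The documents do not support this. It would need RMC-4630 to be held and to clear before osimertinib, and neither elimination rate is readable. Nor do they support the inference that osimertinib is not measured, given the sampling tables listed for that arm and the redactions.

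**Conclusion.** The point holds as a minor error in the text of a safety procedure. Step 3 omits 1 of the 3 drugs in the overdose definition. In arm 2, after an overdose of osimertinib alone, the stated endpoint follows a drug that was not overdosed. It does not hold for every osimertinib overdose: if RMC-4630 is overdosed as well, the endpoint follows one of the two drugs.

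Confidence is high for the omission, which is in unredacted text. No confidence attaches to any consequence, because overdose frequency, half-lives and the status of an osimertinib assay are all unknown. The conclusion assumes only that nothing in the redacted sections overrides step 3.

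**What to change.** In step 3, replace "until RMC-4630 and/or cobimetinib can no longer be detected systemically" with wording to this effect: *until the study drug(s) involved in the overdose (RMC-4630, cobimetinib and/or osimertinib) can no longer be detected systemically*.

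The sponsor should also confirm whether osimertinib is assayed in arm 2. Only if it is not should step 3 add a fixed monitoring period for osimertinib. The sponsor would set its length, because the documents give no basis for a number.

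The cost is one phrase in the next amendment. Close monitoring after an osimertinib overdose may last longer than under the current wording. If the drug is not assayed, the fixed period avoids the need for a new assay.

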**8.5. Pharmacokinetics**

[Redacted text block containing multiple lines of blacked-out content]

[Redacted]

[Redacted]

[Redacted]

[Redacted]

**8.6. Pharmacodynamics**

[Redacted]

[Redacted]

[Redacted]

[Redacted]

[Redacted]

[Redacted]

[Redacted]

[Redacted]

[Redacted]

[Redacted]

[Redacted]

**8.8. Other Biomarkers**

[Redacted]

[Redacted]

[Redacted]

[Redacted]

[Redacted]

[Redacted]

## 8.9. Health Economics and Medical Resource Utilization

Health Economics/Medical Resource Utilization and Health Economics parameters are not evaluated in this study.

## 9. STATISTICAL CONSIDERATIONS

This is a 2-arm, Phase 1b/2 dose-escalation study designed to assess safety, to define an MTD and a recommended dose and regimen for a phase 2 study, and to obtain a preliminary assessment of efficacy of RMC-4630 in combination with cobimetinib in 1 arm and RMC-4630 in combination with osimertinib in the 2nd arm in adult participants with relapsed/refractory solid tumors. The emphasis will be on safety evaluation and any efficacy analyses will be an estimation of the treatment effect. Descriptive statistics will be used to summarize baseline demographic and disease characteristics, treatment administration, efficacy and safety outcomes, as well as PK and PD outcomes.

Descriptive summaries of discrete data will present the number of study participants and the incidence as a frequency and as a percentage. Descriptive summaries of continuous data will present the group mean, standard deviation, median, minimum, maximum, and sample size.

### 9.1. Statistical Hypotheses

There are no formal hypotheses to be tested in this study.

### 9.2. Sample Size Determination

Both arms of the study will include two components: a Dose-Escalation Component and a Dose-Expansion Component consisting of 6 genotypic/histotypic cohorts.

Doses for both RMC-4630 and cobimetinib will vary in dose escalation component of arm 1. Dose escalation recommendations will be conducted using a CRM model for RMC-4630 and cobimetinib arm ([Appendix 10](#)). [Table 1](#) illustrates sample size estimation based on “Scenario 1” depicted in [Figure 2](#). The study is expected to enroll approximately 144 participants as follows:

- Up to 42 participants during the Dose-Escalation Component, assumes 7 total combination dose cohorts (RMC-4630 dosed twice weekly on D1, D4 or D1, D2 with cobimetinib dosed once daily on 21/7 schedule; RMC-4630 and cobimetinib dosed twice weekly on D1, D2) with 3 to 6 participants per dose. The MTD cohort will enroll at least 6 participants.
- After reaching threshold of activity and achieving DLT clearance at a dose level, at least 24 additional participants may be enrolled during expansion prior to RP2D for a maximum 12 participants per dose level (assumes 4 combination dose expansion cohorts).

- Up to 90 participants (15 per class of mutation x 6 strata) will be enrolled at RP2D (combination dose level 4a). Assuming 12 participants are already enrolled during dose escalation and expansion into cohort that will be declared RP2D, additional 78 participants will be enrolled into RP2D cohort.

The primary objective of this study is safety evaluation. The objective the efficacy evaluation is to generate data which will enable a preliminary estimation of the treatment effect. The treatment effect will be interpreted in the clinical context of specific genotypes and histotypes. The target disease stabilization rate is 30%. If 5 out of 15 participants have achieved disease stabilization, the observed disease stabilization rate would be 33% where the lower limit of the 95% CI is 12%, which excludes a null rate of 10%. A sample size of 15 will provide preliminary evidence of efficacy of RMC-4630 and cobimetinib. Replacement of efficacy unevaluable participants at RP2D may be considered.

With a sample size of 144 study participants, the probability of observing 1 or more instances of a specific AE with a true incidence rate of 1%, 2%, or 5% is 76%, 95%, or >99%, respectively.

Only dose for RMC-4630 may vary in dose escalation component of arm 2, while dose of osimertinib will remain constant at 80 mg once daily. Dose escalation/de-escalation recommendations will be following mTPI-2 design for RMC-4630 and osimertinib arm.

- Up to 18 participants during the Dose-Escalation Component, assumes up to 3 total combination dose cohorts with maximum of 6 participants per dose cohort. The MTD cohort will enroll at least 6 participants.
- After reaching threshold of activity and achieving DLT clearance at a dose level, 6-18 participants may be enrolled in the dose expansion cohort for a total of 24 participant in RMC-4630 and osimertinib arm 2 of the study.

### 9.3. Populations for Analyses

For purposes of analysis, the following populations are defined in Table 15.

**Table 15 Population Definitions**

Population	Description
Enrolled	All participants who sign an ICF and meet eligibility criteria
Treated	All participants who take at least 1 dose of study intervention
Evaluable	
Evaluable for DLT: All participants in the treated population who have completed the DLT period or who have discontinued due to AEs or death (unless relationship to RMC-4630 and cobimetinib can be ruled out) prior to the end of the DLT period. In addition, participants must receive at least 75% of planned dose (not miss <math>\geq 3</math> doses of RMC-4630 and cobimetinib on D1D2 intermittent schedule and <math>\geq 6</math> doses of cobimetinib on 21 on/7 off schedule, and <math>\geq 8</math> doses of osimertinib within the DLT window for reasons other than toxicity). This population will be the primary population for fitting the dose-toxicity model.
 
Evaluable for efficacy: All participants with measurable disease at baseline, who take at least 1 dose of study intervention and underwent one post-baseline response assessment or who die or had clinical progression prior to first post-baseline response assessment

Safety	All participants who take at least 1 dose of study intervention

Abbreviations: AE, adverse event; DLT, dose-limiting toxicity; ICF, informed consent form.

